4.1. Inclusion Criteria

Patient eligibility should be reviewed and documented by an appropriate member of the investigator's study team before patients are included in the study.

Patients must meet all of the following inclusion criteria to be eligible for enrollment into the study:

1. Diagnosis:
 - a. Histologically confirmed, unresectable locally advanced or metastatic transitional cell carcinoma of the urothelium.
 - b. Documented Stage IV disease (per American Joint Committee on Cancer/International Union for Cancer Control Tumor Node Metastasis (TNM) system, 7th edition)⁶⁵ at the start of first-line chemotherapy.
 - c. Measurable disease prior to the start of first-line chemotherapy by RECIST v1.1.
2. Prior first-line chemotherapy must have consisted of at least 4 cycles and no more than 6 cycles of gemcitabine + cisplatin and/or gemcitabine + carboplatin. No other chemotherapy regimens are allowed in this study.
 - a. The last dose of first-line chemotherapy must have been received no less than 4 weeks, and no more than 10 weeks, prior to randomization in the present study.
3. Patients without progressive disease as per RECIST v1.1 guidelines (ie, with an ongoing CR, PR, or SD) following completion of 4 to 6 cycles of first-line chemotherapy.
 - a. Eligibility based on this criterion will be determined by investigator review of pre-chemotherapy and post-chemotherapy radiological assessments (CT/MRI scans); see Study Overview, [Section 3.1](#).
4. Provision of a recent formalin-fixed, paraffin-embedded (FFPE) tumor tissue block (or subsection thereof) from the most recent primary or metastatic tumor biopsy or resection obtained prior to treatment with first line chemotherapy but within 24 months prior to randomization, with no intervening systemic anti-cancer therapy. If a FFPE tissue block cannot be provided, 15 freshly cut unstained slides (10 minimum) will be acceptable.

If a suitable tissue sample is not otherwise available, then a *de novo* biopsy (core needle or excisional) must have been obtained for research purposes prior to randomization in this study.

Note: tumor tissue from cytologic sampling (eg, fine needle aspiration, including FFPE cell pellet material) or bone metastases are not acceptable and should not be submitted.

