4.2. Exclusion Criteria

Patients with any of the following characteristics/conditions will not be included in the study:

1. Patients whose disease progressed by RECIST v1.1 on or after first-line chemotherapy for urothelial cancer.
2. Prior adjuvant or neoadjuvant systemic therapy within 12 months of randomization.

3. Prior immunotherapy with IL-2, IFN- α , or an anti-PD-1, anti-PD-L1, anti-PD-L2, anti-CD137, or CTLA-4 antibody (including ipilimumab), or any other antibody or drug specifically targeting T-cell co-stimulation or immune checkpoint pathways.
4. Major surgery ≤ 4 weeks or major radiation therapy ≤ 2 weeks prior to randomization. Prior palliative radiotherapy is permitted, provided it has been completed at least 48 hours prior to patient randomization.
5. Patients with known symptomatic central nervous system (CNS) metastases requiring steroids. Patients with previously diagnosed CNS metastases are eligible if they have completed their treatment and have recovered from the acute effects of radiation therapy or surgery prior to randomization, have discontinued corticosteroid treatment for these metastases for at least 4 weeks, and are neurologically stable.
6. Persisting toxicity related to prior therapy NCI CTCAE v4.0 Grade >1 ; however, alopecia, sensory neuropathy Grade ≤ 2 is acceptable, or other Grade ≤ 2 adverse events not constituting a safety risk based on the investigator's judgment are acceptable.
7. Diagnosis of any other malignancy within 5 years prior to randomization, except for adequately treated basal cell or squamous cell skin cancer, or carcinoma in situ of the breast or of the cervix, low-grade (Gleason ≤ 6) prostate cancer on surveillance without any plans for treatment intervention (eg, surgery, radiation, or castration), or prostate cancer that has been adequately treated with prostatectomy or radiotherapy and currently with no evidence of disease or symptoms.
8. Participation in other studies involving investigational drug(s) within 4 weeks prior to randomization. Observational studies are permitted.
9. Active autoimmune disease that might deteriorate when receiving an immunostimulatory agent. Patients with diabetes type I, vitiligo, psoriasis, or hypo- or hyperthyroid disease not requiring immunosuppressive treatment are eligible.

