9.2.2. Per-Protocol Analysis Set

The Per-Protocol Analysis Set is a subset of the Full Analysis Set and will include patients who receive at least 1 dose of study treatment or who only receive BSC and do not have major protocol deviations expected to impact the primary objectives of the study. Major protocol deviations will be pre-specified in the SAP. The Per-Protocol Analysis Set will be used for sensitivity analyses for the primary efficacy endpoint.

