4.3. Other Analysis Set

4.3.1. Per-protocol analysis set

The per-protocol (PP) analysis set is a subset of the FAS and will include patients who do not meet any of the following criteria that could impact the key objectives of the study. Patients who meet any of the following criteria will be excluded from the PP analysis set.

- Patients randomized to Arm A who did not receive at least one dose of avelumab
- Patients randomized to Arm B who were treated with avelumab

- Baseline ECOG status ≥ 2
- Patient does not meet inclusion criteria 1, 2, or 3 and patient meets exclusion criterion 1

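### Read literally, the per-protocol eligibility exclusion in SAP 4.3.1 removes only patients who progressed, because its two conditions are joined by 'and'

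*SAP*

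**What the plan says.** Protocol 9.2.2 defines the PP set as full-analysis-set patients who were treated (or had BSC only) and who "do not have major protocol deviations expected to impact the primary objectives of the study". It leaves the list of those deviations to the SAP.

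SAP 4.3.1 supplies the list. Its lead-in is "Patients who meet any of the following criteria will be excluded from the PP analysis set", so any single bullet is enough to exclude. The first three bullets cover Arm A patients never given avelumab, Arm B patients who were given it, and baseline ECOG status of 2 or more. The fourth is the only one on disease and prior-treatment eligibility: "Patient does not meet inclusion criteria 1, 2, or 3 and patient meets exclusion criterion 1".

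The criteria it refers to are in Protocol 4.1 and 4.2:

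- Inclusion 1, disease: "Histologically confirmed, unresectable locally advanced or metastatic transitional cell carcinoma of the urothelium", together with Stage IV disease at the start of chemotherapy and measurable disease before it.
- Inclusion 2, chemotherapy: "Prior first-line chemotherapy must have consisted of at least 4 cycles and no more than 6 cycles" of the two permitted gemcitabine-platinum combinations. Item 2a adds the interval: "The last dose of first-line chemotherapy must have been received no less than 4 weeks, and no more than 10 weeks, prior to randomization".
- Inclusion 3, response status: "Patients without progressive disease as per RECIST v1.1 guidelines (ie, with an ongoing CR, PR, or SD"), after those cycles.
- Exclusion 1: "Patients whose disease progressed by RECIST v1.1 on or after first-line chemotherapy for urothelial cancer".

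The PP set is used to repeat the primary OS analysis (Protocol 9.3 and 9.3.1; SAP 6.2.2.2).

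**The concern.** The lead-in makes the bullets alternatives, but inside the fourth bullet the two halves are joined by *and*. As logic, the bullet fires only when a patient fails one of three inclusion criteria **and also** has progressed. A programmer working from this sentence would keep a non-progressed patient with the wrong histology, a patient given another regimen or too few cycles, and a patient randomized outside the 4 to 10 week window. None of the other bullets would remove them.

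Inclusion criteria 1 to 3 are what define the maintenance population named in the primary objective. Protocol 1.3 itself points out that benefit was shown in patients whose chemotherapy had ended 4 to 10 weeks before randomization. The PP analysis is the planned check that the OS result holds once patients who do not belong to that population are set aside. If most forms of ineligibility cannot trigger removal, the check does less than Protocol 9.2.2 asks of it.

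**Working it through.** The plan states no figure here, so there is nothing to reproduce. The check is a truth table.

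**Inputs.** Four yes/no indicators, all from Protocol 4.1 and 4.2:

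- F1, F2, F3: the patient fails inclusion 1, 2, 3.
- E1: the patient meets exclusion 1.

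**Constraint.** A patient whose disease has progressed does not have an ongoing CR, PR or SD, so E1 implies F3. The reverse does not hold: a patient whose response status was never established can fail inclusion 3 without documented progression.

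**Number of feasible patterns.** Four indicators give 2 × 2 × 2 × 2 = 16 patterns. The constraint rules out those with E1 true and F3 false, which number 2 × 2 = 4. That leaves 16 − 4 = 12.

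**Rules compared.**

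- As written: (F1 or F2 or F3) **and** E1.
- Alternative: (F1 or F2 or F3) **or** E1.

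| Group of patterns | Patterns | Excluded by *and* | Excluded by *or* |
|---|---|---|---|
| Fully eligible | 1 | 0 | 0 |
| Passes inclusion 3; fails 1 only, 2 only, or both | 3 | 0 | 3 |
| Fails inclusion 3 without progression, with or without failing 1 and 2 | 4 | 0 | 4 |
| Fails inclusion 3 with progression, with or without failing 1 and 2 | 4 | 4 | 4 |
| **Total** | **12** | **4** | **11** |

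**Results.**

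- In all 12 patterns the rule as written gives the same answer as E1 alone. Because E1 already implies F3, the first half of the bullet is always true when the second half is, and naming inclusion 1, 2 and 3 has no effect.
- The *or* rule removes every pattern except the fully eligible one. The difference is 11 − 4 = 7 ineligible patterns kept by the rule as written.

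**Sensitivity to the constraint.** If E1 is not assumed to imply F3, all 16 patterns are allowed. The *and* rule then excludes 7 and the *or* rule 15. All 7 have E1 true, so under either assumption the bullet cannot remove a patient who has not progressed.

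**Is the gap covered elsewhere?** The other three PP bullets do not touch inclusion 1, 2 or 3. SAP 6.5.2.2 reports patients dosed despite failing inclusion criteria, but does not take them out of the PP set.

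**The case against.** The best counter-argument is that *and* here is ordinary prose joining two lists of disqualifying conditions. That reading has real support. It gives the reference to inclusion 1, 2 and 3 something to do, and the SAP version history says the PP definition was revised to follow the key eligibility criteria. It may well be what the authors meant. It does not remove the point, because the sentence does not say it and the code will be written from the sentence. It also leads to the same clearer wording.

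Second, SAP section 4 requires every patient's analysis-set membership to be assessed and documented before the database is released, and SAP 6.5.2.2 makes eligibility deviations visible. Both give someone a chance to notice a literal coding. Neither changes the rule against which membership is judged.

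Third, nothing decisive depends on the PP set. The primary and interim OS analyses use the full analysis set, success is defined on those tests, and SAP 6.2.2.2 calls the OS sensitivity analyses purely exploratory. This stands and limits the weight of the point.

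Three stronger readings are tempting, and the documents do not support them:

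- A reader might treat failing inclusion 3 and meeting exclusion 1 as the same event. Only one direction holds. The full equivalence would miss the patients who fail inclusion 3 without documented progression, who are also kept.
- A reader might take 7 of 11 ineligible patterns to mean that most ineligible patients are kept. Patterns are not patients, and the number of affected patients could be zero.
- A reader might conclude that the PP result overstates robustness. Keeping these patients brings the PP set closer in membership to the full analysis set, but nothing in the documents shows that the OS estimate would shift.

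**Conclusion.** The point holds as a specification error in the PP definition. Followed literally, the fourth bullet reduces to exclusion 1 and retains 7 of the 11 ineligible patterns. That does not deliver the exclusion of major deviations that Protocol 9.2.2 hands to the SAP.

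Its reach is limited to the PP sensitivity analysis of OS. The primary estimate, the type I error, the power and the stopping boundaries are unaffected. What is lost is part of the PP analysis's value as a check on ineligible enrolment, and the documents do not allow that loss to be sized.

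The pattern counts assume that progression implies failure of inclusion 3. The conclusion that no non-progressed patient can be removed by this bullet does not need that assumption. Both assume that the criterion numbers in the SAP refer to Protocol 4.1 and 4.2 as they now stand. Whether the code follows the literal or the intended reading cannot be seen from the documents.

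**What to change.** Replace the fourth bullet of SAP 4.3.1 with: *Patient does not meet inclusion criterion 1, 2 or 3, or patient meets exclusion criterion 1.* Splitting it into two bullets does the same, since the lead-in already makes bullets alternatives. Then confirm that the analysis-set code matches.

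The cost is one word in the SAP and a check of one line of code. The PP set may become smaller; by how much depends on deviation counts that the documents do not give. No other analysis changes.

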4.3.2. PK analysis sets

The PK concentration analysis set is a subset of the safety analysis set and will include patients who have at least one post-dose concentration measurement above the lower limit of quantitation (LLQ) for avelumab.

The PK parameter analysis set is a subset of the PK concentration analysis set and will include patients who have at least one of the PK parameters of interest for avelumab.

4.3.3. Biomarker analysis set

The biomarker analysis set is a subset of the safety analysis set and will include patients who have at least one baseline biomarker assessment performed.

4.3.4. Immunogenicity analysis set

The immunogenicity analysis set is a subset of the safety analysis set and will include patients who have at least one ADA/nAb sample collected for avelumab in Arm A.

5. GENERAL METHODOLOGY AND CONVENTIONS

5.1. Hypotheses and Decision Rules

5.1.1. Hypotheses and sample size determination

The study is designed to test, in parallel, the following hypotheses:

$$H_{0 \text{ All patients}}: HR_{OS (Arm A/Arm B)} \geq 1, \text{ versus } H_{a \text{ All patients}}: HR_{OS (Arm A/Arm B)} < 1$$

$$H_{0 \text{ PD-L1+}}: HR_{OS (Arm A/Arm B)} \geq 1, \text{ versus } H_{a \text{ PD-L1+}}: HR_{OS (Arm A/Arm B)} < 1$$

where HR_{OS} represents the hazard ratio for OS in the experimental arm vs the control arm.

Approximately 668 patients will be randomized to the treatment arms using a 1:1 randomization, stratified by best response to chemotherapy (CR or PR vs. SD) and site of metastasis (visceral vs. non-visceral) at time of initiating first-line chemotherapy. The type 1 error rate will be split between the co-primary populations to preserve the overall type 1 error rate for the study at 0.025 one-sided. It is estimated that at least 50% of the randomized patients will have adequate tissue for analysis and be determined to have PD-L1-positive tumors.

The sample size for this study is determined based on the following assumptions:

- For all patients and patients with PD-L1-positive tumors receiving BSC alone after first-line chemotherapy, the median OS is 12 months (Powles et al, 2015).
- For all patients receiving avelumab + BSC after first-line chemotherapy, the median OS is assumed to be 17.1 months.

- For patients with PD-L1-positive tumors receiving avelumab + BSC after first-line chemotherapy, the median OS is assumed to be 18.5 months.

This corresponds to a hazard ratio (HR) of 0.7 for all patients and 0.65 for patients with PD-L1-positive tumors under the exponential model assumption.

For all patients, if the true HR is 0.7 under the alternative hypothesis, a total of 425 OS events will be required to have 93% power to detect a HR of 0.7 using a one-sided log rank test at a significance level of 0.015 and a 2-look group-sequential design with Lan-DeMets (O'Brien-Fleming) α -spending function to determine the efficacy boundary and a Gamma Family (-8) β -spending function to determine the non-binding futility boundary.

For patients with PD-L1-positive tumors, if the true HR is 0.65 under the alternative hypothesis, then a total of 219 OS events will be required to have 80% power to detect a HR of 0.65 using a one-sided log rank test at a significance level of 0.01 and a 2-look group sequential design with Lan-DeMets (O'Brien-Fleming) α -spending function to determine the efficacy boundary and a Gamma Family (-8) β -spending function to determine the non-binding futility boundary.

The sample size further assumes a 5% drop-out rate for OS on either treatment arm, a non-uniform patient accrual accomplished over a 28-month period. The data cut-off for the primary OS analysis will occur after the target number of events has been reached in both co-primary populations and the last patient randomized in the study has been followed for at least 12 months after randomization.

5.1.2. Decision rules

To protect the integrity of the study and to preserve the type I error rate, a fraction of alpha for efficacy will be spent at the interim analysis and accounted for in the overall type I error rate (if the interim analysis is performed exactly at the planned number of OS events, alpha spent at interim is 0.005 for all patients and 0.002 for patients with PD-L1-positive tumors). The significance levels for the interim and final efficacy analyses of OS will be determined by using the Lan-DeMets procedure with an O'Brien-Fleming stopping boundary. The overall significance level for the efficacy analysis of OS will be preserved at (one-sided) 0.015 for all patients and 0.01 for patients with PD-L1-positive tumors.

Two analyses will be performed for OS:

The interim analysis of OS will be performed after at least 315 of all randomized patients have died (74% of the target number of OS events for the 'all patients' population), and all of the following conditions have been met:

- 1) all initially planned patients have been randomized, and
- 2) at least 146 patients with PD-L1-positive tumors have died (approximately 66.7% of the total OS events expected in the 'patients with PD-L1-positive tumors' population).

The primary analysis of OS will be performed after at least 425 of all randomized patients and at least 219 patients with PD-L1-positive tumors have died, and the last patient randomized in the study has been followed for at least 12 months after randomization.

The study will have met its primary objective if the experimental arm is statistically significantly superior to the control arm for either one of the co-primary populations, either at the time of the interim analysis or at the time of the final analysis.

The efficacy and futility boundaries for the co-primary populations with the planned number of events at interim look are listed below in Table 5. The boundary values will be updated using the pre-specified α - and β -spending functions with the observed number of events at the time of the interim analysis. If the value of the test statistic for OS exceeds the efficacy boundary, then the experimental arm may be declared statistically significantly superior to the control arm (in the ‘all patients’ or ‘patients with PD-L1-positive tumors’ populations). If the value of the test statistic for OS exceeds the futility boundary, the study may be stopped for futility. Alternatively, as appropriate, the sample size of the study may be adjusted using the method outlined by Cui et al (1999). If the results of the interim analysis indicate serious safety concerns, the sponsor, in conjunction with the External Data Monitoring Committee (E-DMC), will communicate with the Health Authorities regarding stopping the clinical trial.

Table 5. Stopping Boundaries for Overall Survival

Population	Number of Events	Efficacy		Futility	
		Z scale	p-value (one-sided)	Z scale	p-value (one-sided)
All patients	315	$z < -2.595$	$p < 0.005$	$z > -0.789$	$p > 0.215$
Patients with PD-L1-positive tumors	146	$z < -2.947$	$p < 0.002$	$z > -0.397$	$p > 0.346$

Since the observed number of events at the interim analysis for each comparison may not be exactly equal to the planned number of OS events for that comparison, the efficacy and futility boundaries will be updated based on the actual number of observed events using the pre-specified α - and β -spending functions. Therefore, the observed Z-test statistic at the interim analysis will be compared with the updated efficacy and futility boundaries. If the study continues to final analysis, the p-value that will be used to declare statistical significance at the final analysis will be based on the actual number of OS events documented at the cut-off date for the final analysis and the α already spent at the interim analysis. Therefore, if the interim analysis occurs exactly after 315 events for all patients and 146 events for patients with PD-L1-positive tumors, and the study continues until the final analysis, the observed p-value for the comparison will have to be < 0.014 for all patients and < 0.009 for patients with PD-L1-positive tumors to declare statistical significance for that population. If the number of events in the final analysis deviates from the expected number of events, the final analysis criterion will be determined so that the overall significance level across all analyses is maintained at one-sided 0.025.

Based on the stopping boundaries, the timing of interim analysis and information fractions defined above the design has the following operating characteristics.

Table 6. Simulated cumulative probabilities to stop for futility at the interim or final OS analysis

Scenario	Look	Number of OS events	Calendar Time (months)	P(Reject H_{0i})	P(Reject H_{ai})
$H_{0 \text{ All patients}}$ is true (HR=1)	Interim	315	29	0.0051	0.7817
	Final	425	36	0.0163	0.9837
$H_{a \text{ All patients}}$ is true (HR=0.7)	Interim	315	31	0.7039	0.0098
	Final	425	39	0.9257	0.0743
Simulations performed in EAST 6 with number of simulations = 10,000 and seed (H_0, H_a)=3637647, 15346244					
$H_{0 \text{ PD-L1+}}$ is true (HR=1)	Interim	146	28	0.0008	0.6576
	Final	219	37	0.0100	0.9900
$H_{a \text{ PD-L1+}}$ is true (HR=0.65)	Interim	146	30	0.3670	0.0136
	Final	219	41	0.8066	0.1934
Simulations performed in EAST 6 with number of simulations = 10,000 and seed (H_0, H_a)=15459942, 15509960. The actual Interim Analysis and Final Analysis will occur at the same calendar time for both patient populations corresponding to the latest of achieving the target number of events in each population.					

5.2. General Methods

As described in Section 3.4, in this study ‘**treatment arm**’ refers to one of the following:

- Arm A = Avelumab + BSC;
- Arm B = BSC alone.

Endpoints will be summarized based on the analysis sets described in Table 4 by treatment arm, unless otherwise specified.

5.2.1. Data handling after the cut-off date

Data after the cut-off date may not undergo the cleaning process and will not be displayed in any listings or used for summary statistics, statistical analyses or imputations.

